10.6 Analyses

All statistical tests will be two-sided with a nominal alpha level of 0.05. No adjustment for multiple testing will be performed. Stratification will be taken into account in all analyses unless stated otherwise.

Since the goal of the study is to determine the biological activity of CVC on vascular inflammation, the primary analytic approach will be per protocol and limited to participants who remain on study treatment without change in background ART drug class per the study design.

Baseline is defined as pre-entry for TBR and SUV, average of entry and pre-entry for immunology markers, and entry for all other outcome measures.

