10.6.1 Analysis Sets

Per-protocol population is defined as all participants who receive study treatment over 22 weeks and remain on the same ART drug class during the entire study period.

Safety analysis population is defined as all participants who initiated study treatment.

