2.3.1 Primary Objective and Estimand

See Section 3.1 for details about TBR-related terms.

Primary Objective 1: To assess whether CVC treatment results in reduced arterial inflammation by comparing the changes in arterial target-to-background ratio (TBR) in the carotid arteries and aorta after treatment with CVC versus placebo.	
Estimand description	Percentage change in the arterial 18-FDG-PET TBR in the most diseased segment (MDS) of the carotid arteries and aorta following 24 weeks of CVC therapy among virally suppressed people living with HIV with at least one cardiovascular risk factor.
Treatment	Addition of CVC to background ART compared to ART alone.
Target population	Analysis set
Individuals living with HIV who are ≥ 45 years old, have at least one cardiovascular risk factor, and are on stable NNRTI-based or unboosted INSTI-based ART regimen, with suppressed HIV-1 RNA for ≥ 48 weeks prior to CVC start and who remain on the same ART drug class over an additional 24 weeks of CVC.	Participants who remain on study treatment for at least 22 weeks, and remain on the same ART drug class during the study.
Variable(s)	Outcome measure(s)
Fold change in 18-FDG-PET TBR, measured in the MDS of the most diseased vessel between the left and right carotid arteries and aorta over 24 weeks of CVC treatment	Fold change from baseline to week 24 in 18-FDG-PET TBR of the MDS of the most diseased vessel between the left and right carotid arteries and aorta. MDS TBR will be \log_{10} transformed ($\log_{10}[\text{week 24}] - \log_{10}[\text{pre-entry}]$) for analysis and back transformed for a fold change interpretation.
Handling of intercurrent events	Handling of missing data
The following intercurrent events are relevant to the estimand: - Change in background ART regimen not within the same drug class: excluded (principal stratum) - Change in background ART regimen within the same drug class: ignored (treatment policy) - Treatment interruption or missed doses: ignored (treatment policy) - Permanent discontinuation of treatment or background ART: Excluded (principal stratum) - Death – excluded (principal stratum) - Prohibited medications – excluded (principal stratum) - Pregnancy or breast-feeding – excluded (principal stratum)	Missing data due to unreadable or missed scans will be handled by using multiple imputation. A sensitivity analysis for the primary analysis will include complete case analysis.
Population-level summary statistic	Analysis approach

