2.4 Overview of Sample Size Considerations

The target sample size is 75 participants (50 in the CVC arm and 25 in the placebo arm) with baseline and follow-up PET/CT. To allow for some loss to follow-up and participants unwilling or unable to complete 2 scans, the study planned to enroll 93 participants (62 in the CVC arm and 31 in the placebo arm). Final enrollment was 110 participants.

The primary analysis will focus on between-treatment arm differences in the within-participant changes in arterial MDS TBR (the measure of arterial inflammation by PET/CT). Based on a superiority trial design with two-sided $\alpha=0.05$, assuming a standard deviation (SD) of 0.065 \log_{10} TBR for change in MDS TBR, a total of 75 participants providing complete, evaluable data sets will ensure 80% power to detect a between-groups difference of 0.046 \log_{10} MDS TBR (which is a 10% reduction from baseline).

The assumptions underlying the power calculation are as follows:

- 1) The target effect size for the change in MDS TBR on therapy of 10% is based on the observation of a statin intensification study.
- 2) The assumed SD for change in (\log_{10}) MDS TBR of 0.065 is derived from the placebo arm of ACTG A5314.

3) The use of a two-sided, two-sample T-test with type-I error rate of 5%.

The assumption that 93 enrolled participants will provide 75 participants with evaluable data is derived by 20% total data loss due to drop-out after randomization (including premature discontinuation of study treatment and change in background ART drug class).

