4.1.2 Participant Exclusions

Participants who had any events below will be excluded from efficacy data to be analyzed, per handling of intercurrent events (Section 2.3.1):

- Never started treatment
- Deemed clinically ineligible for the study
- Took prohibited medication(s) during the study
- Died
- Became pregnant

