4.1.4 Analysis Sets

Efficacy set (per-protocol set): All eligible participants who remain on study treatment for at least 22 weeks and remain on the same ART drug class during their entire study period.

Complete-case set: Efficacy set participants who have baseline-week 24 pair of PET/CT scan data.

Supplementary efficacy set one: All eligible participants in the efficacy set as well as participants who remained on study treatment for at least 12 weeks and remained on the same ART drug class during their entire study period.

Supplementary efficacy set two: All eligible participants in the efficacy set excluding participants with confirmed HIV-1 RNA > 200 copies/mL or ≥ 14 consecutive days of ART interruption at any time during the course of the study.

Safety set: All enrolled participants who initiate study treatment.

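### SAP 2.3.1 labels exclusion on observed post-randomisation events a principal-stratum strategy, and no planned TBR, SUV or biomarker comparison is free of that selection

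*SAP*

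**What the plan says.** The intercurrent-event list in SAP 2.3.1 includes "Permanent discontinuation of treatment or background ART: Excluded (principal stratum". The same strategy is named for a between-class ART change, death, prohibited medications, and pregnancy or breast-feeding. Treatment interruptions, missed doses and within-class ART changes are handled by treatment policy.

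SAP 4.1.2 puts this into practice. Participants with listed events "will be excluded from efficacy data to be analyzed, per handling of intercurrent events", and one listed event is "Took prohibited medication(s) during the study", with no minimum duration. Protocol 10.6.1 is narrower: "Per-protocol population is defined as all participants who receive study treatment over 22 weeks" and who stay on the same ART class. It does not mention prohibited medication.

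SAP 7.2.3 names four sets for the primary outcome:

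- the efficacy set (at least 22 weeks on treatment, same ART class);
- the complete-case set, a subset of the efficacy set;
- supplementary set one, defined as "All eligible participants in the efficacy set as well as participants who remained on study treatment for at least 12 weeks" on an unchanged ART class;
- supplementary set two, also a subset of the efficacy set.

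SUV outcomes use the efficacy set (SAP 7.4). Biomarkers use the efficacy set and supplementary set one (SAP 8). The Safety set holds everyone who started treatment, but it serves only descriptive summaries and adverse events.

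Protocol 2.1 and 10.6 give the reason for a per-protocol primary analysis: the question is biological activity rather than clinical efficacy.

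**The concern.** A principal stratum is a group defined by what each person would do under either assignment, for example people who would complete treatment on CVC and also on placebo. Membership does not depend on the arm received, so a comparison within the stratum is causal, but it needs an assumption and an estimator to identify the members. Dropping people on what happened under their own arm does something else. CVC participants are kept because they persisted on CVC, and placebo participants because they persisted on placebo. These need not be the same kind of people.

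The SAP's target population shows the gap. It describes people who keep their ART class over 24 weeks of CVC, which is never observed for anyone on placebo.

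Two things are at stake. The label claims a causal status that the analysis has not earned. And if those removed from the CVC arm would have shown less TBR reduction, the contrast would favour CVC, with no planned efficacy analysis that restores the randomised comparison.

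**Working it through.** **1. The plan's own figure.** Inputs from SAP 2.4 and Protocol 10.4 and 10.6: "All statistical tests will be two-sided with a nominal alpha level of 0.05"; "80% power to detect a between-groups difference of 0.046" log10 TBR; "MDS TBR of 0.065 is derived from the placebo arm of ACTG A5314"; 50 + 25 evaluable. The SE is 0.065 × √(1/50 + 1/25) = 0.0159. The exact two-sample t-test gives 81.4% power, so the stated 80% reproduces. No stated number is disputed.

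**2. Which analyses escape the selection.**

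| Comparison | Time on treatment required | Same ART class | SAP 4.1.2 exclusions |
|---|---|---|---|
| Primary TBR; SUV | ≥22 weeks | yes | yes |
| Complete case | ≥22 weeks, plus both scans | yes | yes |
| Supplementary one; biomarkers | ≥12 weeks | yes | yes |
| Supplementary two | ≥22 weeks, less viraemia or long ART interruption | yes | yes |

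Biomarkers are also analysed in the efficacy set. None of these is free of selection after randomisation. Multiple imputation covers unreadable or missed week 24 scans. In the primary analysis it works inside the efficacy set, so it brings back nobody who was excluded. The sensitivity analysis in Protocol 10.6.3 adds only evaluations after week 12 made within 7 days of treatment.

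**3. Size of the possible bias.** Let p be the proportion excluded in each arm, and d the number of SDs by which excluded participants would have done worse than those kept, taken as equal in both arms. The mean in those kept then differs from the mean in all treated by p × d × SD, so

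bias = (p_CVC − p_placebo) × d × 0.065.

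The documents give neither p by arm nor d; both are assumptions. Type I error is the normal tail probability after a shift of bias/SE.

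| Excluded, CVC vs placebo | d | Bias (log10) | Share of 0.046 | Type I error, 50 + 25 kept |
|---|---|---|---|---|
| 20% vs 20% | any | 0 | 0% | 5.0% |
| 20% vs 15% | 0.5 | 0.0016 | 3.5% | 5.1% |
| 20% vs 10% | 0.5 | 0.0033 | 7% | 5.5% |
| 20% vs 0% | 0.5 | 0.0065 | 14% | 6.9% |
| 20% vs 5% | 1.0 | 0.0098 | 21% | 9.4% |

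Third row: 0.10 × 0.5 × 0.065 = 0.00325; 0.00325/0.046 = 7%; 0.00325/0.0159 = 0.20; P(Z > 1.76) + P(Z < −2.16) = 0.055.

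The arm split of the 110 enrolled is not given. If it is about 73 + 37, the third row keeps 58 + 33 and its type I error is 5.6%; the last row keeps 58 + 35 and its figure is 10.8%.

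**4. Are unequal exclusions likely?** The background in Protocol 2.1 points both ways. In AURORA, CVC versus placebo showed nausea in 8.8% vs 6.6%, ALT increase in 3.8% vs 1.5% and AST increase in 3.2% vs 1.0%. These are differences of about 2 points, in events rather than in stopping. In CENTAUR, 121 of 144 in each group went on to Year 2 (61 + 60 = 121 for placebo). In Study 652-2-201 nobody stopped for an adverse event; in Study 652-2-202 one CVC participant did.

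**The case against.** The strongest reply is that per-protocol is a disclosed and reasoned choice for a phase II mechanistic question, and that the plan is not blind to selection. Supplementary set one re-admits people who stopped between weeks 12 and 22. SAP 7.1 tabulates inclusion and exclusion by reason and arm for every efficacy set. SAP 5.3 and 5.7 show exclusions and discontinuations by arm, and SAP 5.5 gives baseline characteristics for both the Safety and efficacy sets. All of this stands. A reader might infer that the plan has no safeguard at all, or that a per-protocol primary analysis is itself the error; the documents support neither. But the tables show whether exclusions are unequal without showing what that does to the estimate, and set one still selects on persistence and ART class.

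The label also changes no number, because the operation is clear from SAP 4.1.2 and 4.1.4. That is true, but it changes what the estimate may be said to mean.

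Prohibited-medication users who stayed on treatment should be few. Protocol 9.1 makes the need for such a drug a reason to stop, and Protocol 5.4.2 treats nirmatrelvir/ritonavir for under 10 days as precautionary and allows midazolam for surgical sedation. This limits the numbers, but the SAP and protocol definitions still differ.

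Finally, an all-treated TBR analysis would rest partly on imputation. Protocol 6.2.4 requires no scan for those who stop before week 12 and drops the week 24 scan for those who have stopped. A gap from the per-protocol result would also mix dilution with selection. Both points stand, and they limit how the added analysis should be read.

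**Conclusion.** The point holds in two parts. First, the principal-stratum label in SAP 2.3.1 does not describe the analysis, which is an on-treatment per-protocol contrast. Second, no TBR, SUV or biomarker comparison is free of post-randomisation selection, and SAP 4.1.2 selects further than Protocol 10.6.1 does.

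The likely consequence is small to moderate: about 0.003 log10 and a type I error near 5.5% in the 20% vs 10%, 0.5 SD case, and nothing if exclusions are alike in both arms. The larger rows of the table are arithmetic on assumed rates; nothing in the documents' discontinuation data supports gaps of that size. A reader might infer from the adverse-event figures that the CVC effect will be overstated. The documents do not show that exclusions will differ by arm or relate to TBR change, so that inference is not supported. This should be corrected, but it does not invalidate the primary analysis.

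**What to change.** Keep the per-protocol primary analysis, and make these changes:

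1. In SAP 2.3.1, replace the label by *excluded on observed events (on-treatment per-protocol contrast)*.
2. Reconcile the prohibited-medication exclusion in SAP 4.1.2 with the analysis set in Protocol 10.6.1.
3. In SAP 4.1.4 and 7.2.3, add one supplementary analysis of the primary outcome in all participants who started study treatment, by randomised arm, regardless of later stopping, ART class change or prohibited medication. Use the week 24 scan, or the discontinuation scan where one exists. State this explicitly, because the week 24 window in SAP 4.1.3 opens only 7 days before that visit. Multiply impute the rest, with a reference-based version that imputes CVC stoppers without a scan from the placebo arm.
4. Run the same set for the biomarkers in SAP 8, where visits continue off treatment and observed values can be used.

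The cost is SAP wording and one further set of models; the primary result is untouched. For TBR, the contribution of those who stop before week 12 depends on the imputation assumption, imputation widens the interval, and a gap from the primary estimate combines dilution and selection. Precision should be workable. If 73 + 37 are treated, with SD 0.065 and no loss from imputation (an optimistic assumption), power is 93.5% for the full 0.046, 87.9% if it is diluted by 10% and 79.4% if diluted by 20%. The per-protocol set at 20% loss (58 + 29) has 86.8%.

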2.3.2 Secondary Objectives

- 1) To assess changes in metabolic parameters including fasting glucose, fasting insulin, homeostasis model assessment-estimated insulin resistance (HOMA-IR), inflammatory markers including high sensitivity interleukin 6 (hsIL-6) and hsCRP, and markers of monocyte/macrophage activation including soluble CD14 (sCD14), soluble CD163 (sCD163), and monocyte chemoattractant protein-1 (MCP-1) after treatment with CVC compared to placebo.
- 2) To assess changes in cellular chemokine receptor 5 (CCR5) and CCR2 levels and changes in their plasma ligands (MIP-1 α , MIP-1 β and RANTES for CCR5; MCP-1 [CCL2] for CCR2) after treatment with CVC compared to placebo.
- 3) To evaluate the safety of CVC in virally suppressed antiretroviral therapy (ART)-treated, HIV-infected individuals.

2.3.3 Exploratory Objectives

- 1) To measure the effects of CVC on adipocytokines (adiponectin) and on noninvasive assessments of liver fibrosis, including AST to Platelet Ratio Index (APRI) and Fibrosis-4 (FIB-4).
- 2) To assess changes in FDG uptake in visceral fat and to quantify changes in visceral adipose tissue area and volume, subcutaneous adipose tissue area and volume, fat density, and liver to spleen attenuation ratio (as a noninvasive measure of hepatosteatosis) by noncontrast CT after treatment with CVC compared to placebo.
- 3) [PK/PD] To determine the association between CVC trough exposure and the primary treatment outcome (i.e., reduced arterial inflammation).
- 4) To evaluate the effects of CVC on markers of monocyte and T cell homing and activation as well as on myeloid cells.
- 5) To assess changes in occupancy of the CCR5 and CCR2 receptors on T cells and monocytes after treatment with CVC compared to placebo.
- 6) [PK/PD] To evaluate potential drug interactions by a) investigating the impact of INSTI- and NNRTI-based ART on CVC trough estimates and to compare these estimates across regimens and b) investigating the impact of CVC treatment versus no treatment on the trough exposure of ART.

Note: The Study Pharmacologist is evaluating currently available data on the effects of CVC on ART exposures to determine ARTs would be of interest for part b) of this objective.

2.4 Overview of Sample Size Considerations

The target sample size is 75 participants (50 in the CVC arm and 25 in the placebo arm) with baseline and follow-up PET/CT. To allow for some loss to follow-up and participants unwilling or unable to complete 2 scans, the study planned to enroll 93 participants (62 in the CVC arm and 31 in the placebo arm). Final enrollment was 110 participants.

The primary analysis will focus on between-treatment arm differences in the within-participant changes in arterial MDS TBR (the measure of arterial inflammation by PET/CT). Based on a superiority trial design with two-sided $\alpha=0.05$, assuming a standard deviation (SD) of 0.065 \log_{10} TBR for change in MDS TBR, a total of 75 participants providing complete, evaluable data sets will ensure 80% power to detect a between-groups difference of 0.046 \log_{10} MDS TBR (which is a 10% reduction from baseline).

The assumptions underlying the power calculation are as follows:

- 1) The target effect size for the change in MDS TBR on therapy of 10% is based on the observation of a statin intensification study.
- 2) The assumed SD for change in (\log_{10}) MDS TBR of 0.065 is derived from the placebo arm of ACTG A5314.

3) The use of a two-sided, two-sample T-test with type-I error rate of 5%.

The assumption that 93 enrolled participants will provide 75 participants with evaluable data is derived by 20% total data loss due to drop-out after randomization (including premature discontinuation of study treatment and change in background ART drug class).

2.5 Timing of Final Analyses

3 Outcome Measures

3.1 Key Definitions Related to FDG-PET Imaging

Term(s)	Definitions at a Participant Level
Target vessel	Specific arterial vessels of interest: R carotid, L carotid, and aorta.
Background vessel	Internal jugular vein (JV) for carotids and superior vena cava (SVC) for aorta.
Standardized Uptake Value (SUV):	Decay-corrected tissue concentration of FDG (in kBq/mL) divided by the injected dose per body weight (kBq/g). SUV is unitless. 1. Target SUV 2. Background SUV 3. Average background SUV
Most diseased segment (MDS)	2-3 slices of arterial segment, centered on the slice of the target vessel with the highest SUV at baseline .
Index Vessel	Vessel with the highest vessel TBR (see definition below) at baseline (i.e., most diseased vessel).
Target-to-Background Ratio (TBR):	Measure of FDG uptake, calculated as a ratio between the target and background SUV. 1. Vessel TBR 2. Vessel MDS TBR 3. Index vessel MDS TBR

3.2 Primary Outcome Measure

Primary Outcome Measure			
	Expected Reporting Timeline	Outcome Measure(s)	Associated Objective(s)
1	CROI	Change in the Index vessel MDS TBR of the index vessel from baseline to week 24	Primary

3.3 Secondary and Other Outcome Measures

Secondary Outcome Measures			
	Expected Reporting Timeline	Outcome Measure(s)	Associated Objective(s)
1	CROI	Change in vessel TBR of the bilateral carotid artery and aorta from baseline to week 24 from baseline to week 24 For the bilateral carotid, the mean of the maxSUV for both the right and left carotid arteries will be combined.	Further investigation of Primary
2	CROI	Change in average vessel SUV of the bilateral carotid artery and aorta from baseline to week 24 For the bilateral carotid, the mean of the maxSUV for both the right and left carotid arteries will be combined.	
3	CROI	Change in fasting glucose from baseline to week 24	Secondary 1
4	FINAL	Change in fasting insulin and HOMA-IR from baseline to week 24	Secondary 1
5	CROI	Change from baseline to week 24 in 
 IL-6, hsCRP, MCP-1 (inflammatory biomarkers) sCD14, sCD163 (markers of monocyte/macrophage activation) 	Secondary 1
6	FINAL	Change from baseline to week 24 in: 
 Cellular levels of CCR5 and CCR2 Plasma levels of RANTES, MIP-1α, MIP-1β (CCR5 plasma ligands) Plasma levels of MCP-1 (CCR2 plasma ligand) 
Note: MCP-1 is the same outcome measure described above, it is retained here as it will be repeated in tabular summaries related to CVC effects on CCR5 and CCR2.
	Secondary 2
7	CROI	
 Occurrence of at least one SAE Occurrence of at least one treatment related AE Occurrence of at least one treatment limiting AE 	Secondary 3
Other Outcome Measures			
	Expected Reporting Timeline	Outcome Measure(s)	Associated Objective(s)
1	FINAL	Change in FDG uptake in visceral fat and lymph nodes from baseline to week 24.	Exploratory 2
2	FINAL	Change in adipocytokines (such as adiponectin) from baseline to week 24.	Exploratory 1

3	FINAL	
Change from baseline to week 24 in myeloid derived suppressor cell (MDSC) frequencies
 
Change from baseline to week 24 in monocyte subsets:
 
 • % CD14+, CD16- (Classical); % CD14+, CD16+ (Inflammatory); % CD14-, CD16+ (Non-classical) where % is % of total monocytes • Expression of CX3CR1, CCR5, CCR2 (homing receptors) on total monocytes and on monocyte subsets. • HLA-DR density and CD69 expression (monocyte activation) on total monocytes and on monocyte subsets. 	Exploratory 4, 5
4	FINAL	
Changes from baseline to week 24 in CD4 and CD8 T cell expression of CX3CR1, CCR2, CCR5
 
Changes from baseline to week 24 in CD4 and CD8 T cell expression CD38 and HLA-DR
	Exploratory 5
5	FINAL	[PK/PD] CVC trough concentration measured at weeks 4, 8, 12, and 24.	Exploratory 3, 6
6	FINAL	[PK/PD] ART trough concentration measured at pre-entry, weeks 4, 8, 12, and 24. Measured only in participants randomized to CVC.	Exploratory 6

4 Statistical Principles

4.1 General Considerations

4.1.1 Data for Analysis

Key Timepoints	
Date	Timepoint
[REDACTED]	[REDACTED]

4.1.2 Participant Exclusions

Participants who had any events below will be excluded from efficacy data to be analyzed, per handling of intercurrent events (Section 2.3.1):

- Never started treatment
- Deemed clinically ineligible for the study
- Took prohibited medication(s) during the study
- Died
- Became pregnant

